For parts A and B, medium or high potency TCS, systemic corticosteroids or nonsteroidal immunosuppressants, or TCI may be provided as rescue treatment to study patients at the discretion of the investigator. The use of rescue treatment is only allowed after day 14 of the study in part B. Investigators will be required to perform an Investigator Global Assessment (IGA) prior to starting rescue treatment and will initiate rescue treatment only in patients who either have an IGA score = 4 or have intolerable symptoms.

Endpoints**Primary:**

The primary endpoints in part A are:

- Concentration of total dupilumab in serum over time and PK parameters (summary statistics of drug concentration and PK parameters)
- The incidence and severity of treatment-emergent adverse events (TEAEs) through the end of part A.

The primary endpoint in part B is the proportion of patients with an IGA score of 0 to 1 (on a 5-point scale) at week 16.

The co-primary endpoints in part B (**only in European Union [EU] and EU Reference Market Countries**):

- Proportion of patients with Eczema Area and Severity Index (EASI)-75 ($\geq 75\%$ improvement from baseline) at week 16
- Proportion of patients with an IGA score of either 0 or 1 (on a 5-point scale) at week 16

Secondary:

The secondary endpoints in part A are:

- The incidence of serious adverse events (SAEs) and severe TEAEs to week 4
- Percent change in EASI score from baseline to week 4
- Percent change in SCORing Atopic Dermatitis (SCORAD) from baseline to week 4
- Proportion of patients with an IGA score of either 0 or 1 (on a 5-point scale) at week 4

Immunogenicity will be addressed by the ADA parameters described in the protocol.

The key secondary endpoints in part B are:

- Proportion of patients with EASI-75 ($\geq 75\%$ improvement from baseline) at week 16 (**not applicable for EU or EU Reference Market Countries**)
- Percent change in EASI score from baseline to week 16
- Percent change from baseline to week 16 in weekly average of daily worst scratch/itch numeric rating scale (NRS) score

Procedures and Assessments

Safety and tolerability will be assessed by vital signs, physical examinations, clinical laboratory tests, and clinical evaluations. Parents/caregivers will be asked to monitor all adverse events (AEs) experienced from the time of informed consent until their last study visit.

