- For lesions persisting or worsening under daily treatment with low potency TCS, patients may be treated (rescued) with medium or high potency TCS (super potent TCS are not allowed to be used, even as rescue, see Section 5.3). The use of medium or high potency TCS as rescue is only allowed after day 14. A medium or high potency TCS should normally be restricted to use on non-delicate skin sites (excluding face, flexures, groin), and should not be used for a prolonged period in order to prevent the development of cutaneous atrophy and adrenal axis suppression. Low potency steroids should normally be used for delicate skin sites (face, flexures, groin) during these flares. Topical calcineurin inhibitors may be used for rescue, alone or in combination with TCS, but the use of TCIs should be reserved for problem areas only (eg, face, neck, intertriginous, and genital areas, etc).

Steroids that can be used during the study are described below and in [Appendix 2](#). The use of TCS should be consistent with the product label. The use of very high potency or super potent TCS is prohibited during the study, as their use is not recommended in patients under 12 years of age. If patients have tolerance issues with any of these steroids, and/or to the excipients in a particular formulation (eg, hypersensitivity), or if they are not commercially available in some countries, they may substitute with products of the same potency from the list provided in the investigator site binder. It is required that patients use hydrocortisone acetate 1% cream for low potency (hydrocortisone 1% cream can be used in case the acetate salt is not available). Only in case of known side effects to hydrocortisone 1% / hydrocortisone acetate 1% cream (eg, for hypersensitivity) or in case of non-availability due to any reason, other low potency TCS such as alclometasone dipropionate 0.05% cream or desonide 0.05% cream can be used.

If rescue with TCS is needed, it is recommended that patients use triamcinolone acetonide 0.1% ointment for medium potency. Other medium to high potency TCS can be used as per investigator discretion. (Please refer to [Appendix 2](#) for a list of such agents).

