- It is required that moisturizers be applied twice daily during the 7 consecutive days immediately before randomization (does not include day of randomization) and patients are to continue to apply moisturizers throughout the study (once in the morning and once in the evening). A 60-minute interval between the application of emollients and TCS is recommended wherever applicable.
- Patients will return TCS tubes at each clinic visit through week 16, and these tubes will be weighed by the site staff to determine the actual amount of TCS used.

5.3. **Rescue Treatments**

Rescue treatment for worsening of AD may be provided to study patients at the discretion of the investigator in parts A and B of the study. The use of rescue treatment is only allowed after day 14 of the study **in part B**. Investigators will be required to perform an IGA assessment prior to starting rescue treatment and initiate rescue treatment only in patients who either have an IGA score ≥ 3 or have intolerable symptoms. If possible, investigators are encouraged to consider rescue initially with topical treatment (eg, medium or high potency TCS) and to escalate to systemic medications only for patients who do not respond adequately after at least 7 days of topical treatment. Topical calcineurin inhibitors may be used for rescue, alone or in combination with TCS, but the use of TCIs should be reserved for problem areas only (eg, face, neck, intertriginous, and genital areas, etc). Investigators may also consider rescue with crisaborole. Rescue treatment for these topical therapies should be used as per prescribing information and local guidelines. Patients may continue study treatment if rescue consists of topical medications.

Patients who receive systemic corticosteroids or systemic non-steroid immunosuppressive drugs (eg, cyclosporine, methotrexate, mycophenolate-mofetil, azathioprine, etc) as rescue medication during part B of the study, will be discontinued permanently from the study drug. All patients will be asked to complete the scheduled study visits and assessments whether or not they complete study treatment and whether or not they receive rescue treatment for AD. Investigators should make every attempt to conduct efficacy and safety assessments (eg, disease severity scores, safety laboratory tests) immediately before administering any rescue treatment. An unscheduled visit may be used for this purpose, if necessary. For the purpose of the efficacy responder analysis, a

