If medically necessary (i.e. to control intolerable AD symptoms), rescue treatment for AD may be provided to study patients at the discretion of the investigator. The use of rescue treatment is only allowed after day 14 of the study. Investigators will be required to perform an IGA assessment prior to starting rescue treatment and initiate rescue treatment only in patients who either have an IGA score  $\geq 3$  or have intolerable symptoms. If possible, investigators are encouraged to consider

rescue initially with topical treatment (e.g., high potency TCS) and to escalate to systemic medications only for patients who do not respond adequately after at least 7 days of topical treatment. Patients may continue study treatment if rescue consists of topical medications. Patients who receive systemic corticosteroids or systemic non-steroidal immunosuppressive drugs (e.g., cyclosporine, methotrexate, mycophenolate-mofetil, azathioprine, etc.) as rescue medication during the study will be discontinued permanently from the study drug. All patients will be asked to complete the scheduled study visits and assessments whether or not they complete study treatment and whether or not they receive rescue treatment for AD. Investigators should make every attempt to conduct efficacy and safety assessments (e.g., disease severity scores, safety laboratory tests) immediately before administering any rescue treatment. An unscheduled visit may be used for this purpose, if necessary. For the purpose of efficacy analysis, patients who receive rescue treatment during the study will be considered treatment failures.

For the purpose of the efficacy responder analysis, a pre-specified algorithm will be used to classify rescue (details in Section 5.6.1). In addition, a blinded review of all post-baseline medications to adjudicate rescue treatment, based on medical judgement, will be performed to adjudicate rescue. Patients who receive rescue treatment as per this adjudication during the study will be considered as treatment failures.

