### 5.6.1. Analysis of Primary/Co-Primary Efficacy Variable

The Cochran-Mantel-Haenszel (CMH) test adjusted by randomization strata (baseline weight group:  $\geq 5$ - $<15$  kg and  $\geq 15$ - $<30$  kg), baseline disease severity (IGA=3 and 4), and region/country (North America, Europe)) will be used for the analysis of percentage of patients with IGA 0 or 1 at week 16. Similar procedures will be used for percentage of patients with EASI-75 at week 16. At the time of this SAP, all patients for this study have been randomized. The smallest stratum (region = EU, baseline weight  $<15$  kg, IGA=3) has 2 subjects only. All other strata have more than 10 patients. In all statistical analysis utilizing stratification factors in CMH test, stratum (region = EU, baseline weight  $<15$  kg, IGA=3) will be combined with the stratum (region = EU, baseline weight  $\geq 15$  kg, IGA=3).

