#### Handling of dropouts or adjudicated rescue treatment or missing value for the binary response variables as the primary analysis:

- If a patient withdraws consent from the study or discontinues due to AE or lack of efficacy (LOE), this patient will be counted as a non-responder for the time points after withdrawal.
- To account for the impact of rescue treatment on the efficacy effect: if rescue treatment is used (see Section 4.3, Appendix 1, and Appendix 6 for rescue treatment), the patient will be specified as a non-responder from the time the rescue treatment is used.
- If the patient has the missing value at week 16 due to any other reasons including COVID-19, the data will be imputed using multiple imputation (MI) based on all observed values as described below:
- The underlying continuous (e.g. EASI) or categorical variable (e.g. IGA) will be imputed 40 times to generate 40 complete data sets by using the SAS procedure MI using the following steps.
  - **Step 1:** The monotone missing pattern is induced by Markov Chain Monte Carlo (MCMC) method in MI procedure using seed number 12345. The monotone missing pattern means that if a patient has missing value for a variable at a visit, then the values at all subsequent visits for the same variable are all missing for the patient.

- **Step 2:** The missing data at subsequent visits will be imputed using the regression method for the monotone pattern with seed number 54321 and adjustment for covariates including treatment groups, randomization strata (baseline weight group, baseline IGA and region), and relevant baseline variables. For the categorical variable, such as IGA, a logistic regression under monotone option will be used.

Based on each imputed data, the response status (responder or non-responder) will be determined for each subject.

Once imputations are made, the week 16 data (binary response) of each of the 40 complete datasets will be analyzed using CMH test. The SAS MIANALYZE procedure will be used to generate valid statistical inferences by combining results from the 40 analyses using Rubin's formula. An appropriate transformation (such as Wilson-Hilferty transformation) of CMH test statistics can be used in Rubin's formula (Ratitch et. al 2013).

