### **5.6.2. Analyses of Secondary Efficacy Variables**

All secondary endpoints will be evaluated based on the FAS population.

The binary secondary efficacy endpoints will be analyzed using the same approaches used for the analysis of the primary endpoints as described in Section 5.6.1.

The continuous endpoints (e.g. EASI, worst scratch/itch NRS score) will be analyzed using analysis of covariance (ANCOVA) model with treatment, randomization strata (baseline weight group:  $\geq 5$ -<15 kg and  $\geq 15$ -<30 kg), baseline disease severity (IGA=3 and 4), region/country (North America, Europe) and relevant baseline value included in the model as the primary analysis method. The missing data for continuous endpoints will be imputed by the pattern-mixture

approach (MI-WOCF Method). The WOCF approach will be used for data after rescue or missing due to withdrawn consent, AE, and lack of efficacy. To be specific, the missing data will be imputed by postbaseline worst-observation-carried-forward (WOCF) if there is at least one non-missing postbaseline value or by baseline value if there is no postbaseline value. The multiple imputation (MI) approach will be used for the missing due to other reasons, including reasons due to COVID-19. The MI will be performed based on all observed data before the imputation by WOCF approach. To account for the uncertainty in the imputation, missing data from the FAS will be imputed 40 times to generate 40 complete data sets by using the SAS procedure MI following the 2 steps below:

**Step 1:** The monotone missing pattern is induced by Markov Chain Monte Carlo (MCMC) method in MI procedure using seed number 12345. The monotone missing pattern means that if a patient has missing value for a variable at a visit, then the values at all subsequent visits for the same variable are all missing for the patient.

**Step 2:** The missing data at subsequent visits will be imputed using the regression method for the monotone pattern with seed number 54321 and adjustment for covariates including treatment groups, randomization strata (baseline weight group, baseline IGA and region), and relevant baseline.

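### The protocol gives two different IGA thresholds for starting rescue, and rescue makes a child a non-responder

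*Protocol*

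**What the plan says.** The synopsis (Rescue Treatment) covers parts A and B. It requires an IGA before rescue and then has investigators "initiate rescue treatment only in patients who either have an IGA score = 4 or have intolerable symptoms". Protocol Section 5.3 (Rescue Treatments) also covers both parts and requires the same prior IGA, but limits rescue to patients who "have an IGA score ≥ 3 or have intolerable symptoms". SAP Section 4.3, which concerns part B only, gives the Section 5.3 threshold. All three allow part B rescue only after day 14.

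Two other protocol passages touch the point without setting a threshold. In Section 5.2 the background regimen says: "For lesions persisting or worsening under daily treatment with low potency TCS, patients may be treated (rescued) with medium or high potency TCS". Section 1.2.1 mentions exacerbations or intolerable symptoms as occasions for rescue.

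The consequences for analysis are in the SAP. Under Section 5.6.1, once rescue is used, "the patient will be specified as a non-responder from the time the rescue treatment is used". For continuous endpoints, Section 5.6.2 says: "The WOCF approach will be used for data after rescue".

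**The concern.** An investigator with a child at IGA 3 whose symptoms are troublesome but not judged intolerable finds opposite instructions in the synopsis and in Section 5.3. Both use restrictive wording, so neither can be read as an example or a suggestion.

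This state is ordinary in the trial. Part B enrols at IGA 3 or 4, about 40 of the planned 160 places may go to children entering at IGA 3, and a child entering at IGA 4 can improve to 3. Under Section 5.3 every enrolled child meets the IGA condition at baseline; under the synopsis those entering at IGA 3 do not.

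Two things are at stake. The first is the care of these children. Section 5.7.1 prohibits medium and high potency TCS and TCI in part B except as rescue, so the threshold also decides whether their use at IGA 3 follows the protocol. The second is the endpoint. Rescue is handled as failure for the binary endpoints, so sites reading different passages could produce different failure rates for the same disease state.

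**Working it through.** The plan gives no figure to reproduce here. The check is a comparison of the rules over all states, followed by a bound on the effect of one child.

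**Comparison of the rules** (part B, after day 14)

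| State | Synopsis | Section 5.3 and SAP 4.3 |
|---|---|---|
| IGA 0 to 2, symptoms not intolerable | not allowed | not allowed |
| IGA 3, symptoms not intolerable | not allowed | allowed |
| IGA 4 | allowed | allowed |
| Any IGA, intolerable symptoms | allowed | allowed |

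The rules differ in exactly one state.

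**Is it a transcription fault or superseded text?** IGA 4 is the top of the scale (Protocol Appendix 3), so a lost inequality sign would not alter the synopsis rule, and the digit itself differs. None of the three statements comes from the amendment history. The Amendment 3 entry on background and rescue treatment lists both the synopsis treatments and Section 5.3 as changed, but records no change of IGA threshold.

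**Does it alter how rescue is classified?** No. SAP Appendix 6 classifies by medication, indication and timing, with adjudication where needed, and has no IGA criterion. The conflict affects which children receive rescue, not how rescue is counted once given.

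**Bound per child.** Inputs are 80 patients per arm and the planned response rates in Protocol Section 9.2.

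- Child who would otherwise have been a week 16 responder: 1/80 = 1.25 percentage points in that arm.
- Child who would not have responded anyway: 0 points.
- Expected shift = 1.25 × response rate, if affected children would have responded at the planned rate for their arm:
  - IGA 0/1, placebo: 1.25 × 0.114 = 0.14 points
  - IGA 0/1, dupilumab: 1.25 × 0.328 = 0.41 points
  - EASI-75, placebo: 1.25 × 0.268 = 0.34 points
  - EASI-75, dupilumab: 1.25 × 0.697 = 0.87 points

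The last step is an assumption. The documents give no response rate for children judged to need rescue at IGA 3.

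**The case against.** The strongest reply is that this is one summary line out of step with the detailed text. Where the protocol body sends the reader elsewhere on rescue, it points to Section 5.3, and the SAP carries the Section 5.3 threshold. That is a fair description, and it makes the synopsis the odd one out. It does not settle the matter, because no passage ranks the synopsis below the body and a site may work from either.

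Other points limit the weight and should be accepted:

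- Part B is randomized and double-blind, so differences between sites in applying the threshold should be unrelated to assignment. No type I error problem follows; what remains is noise or a change in effect size of unknown direction.
- Both rules allow rescue for intolerable symptoms, a term left undefined, so the group in dispute may be small.
- Section 5.2 is silent on IGA and is not a rival threshold. Its relation to Section 5.3 still needs stating.
- SAP Section 4.3 opens by describing medical need in terms of intolerable symptoms before giving its threshold. It should be reconciled along with the rest.
- The per-child figures apply whole-arm rates to children selected for needing rescue, who may respond less often. They are illustrative and may overstate the shift.
- Partial safeguards exist: blinded review of post-baseline medications, summaries of rescue use and time to first rescue, and in Protocol Section 9.5.2.1 an analysis of observed data regardless of rescue. The sensitivity analyses in SAP Section 5.6.1 do not repeat that last one; they give only the tipping-point analysis.

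These points reduce the likely consequence. They do not remove the contradiction.

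**Conclusion.** The concern holds. Current text gives two incompatible thresholds for starting rescue, differing for children at IGA 3 without intolerable symptoms after day 14. The textual finding is certain. The consequence is bounded at 1.25 points per affected child in one arm, with expected values of 0.14 to 0.41 points for IGA 0/1 and 0.34 to 0.87 points for EASI-75 if the planned arm rates apply to these children. The effect on the continuous endpoints was not quantified. No trial-level effect can be given, because the number of affected children is not in the documents and nothing shows that sites followed different passages. It should be corrected, since it is a treatment instruction for infants and young children that also decides who becomes a non-responder. This review takes no position on which threshold is right.

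**What to change.** State one threshold in the synopsis, Protocol Section 5.3 and SAP Section 4.3, and say how Section 5.2, Section 1.2.1 and the opening of the SAP rescue paragraph relate to it. The sponsor decides which rule applies. Notify sites for any children still on treatment; the benefit is limited, because the SAP records: "At the time of this SAP, all patients for this study have been randomized".

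Before unblinding, produce a blinded descriptive listing, by site, of rescue started at IGA 3, with any recorded reason. It documents how the rule was applied and should not be used to reclassify rescue that was actually given.

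The cost is a wording correction, a site notice and one listing. The listing can draw on the IGA already required before rescue. No recorded field for intolerable symptoms is described, so the reason may be missing for some children.

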IgE	Immunoglobulin E
IgG	Immunoglobulin G
IL	Interleukin
IPV	Inactivated polio vaccine
IRB	Institutional Review Board
IV	Intravenous
IWRS	Interactive web response system
LDH	Lactate dehydrogenase
LDL	Low-density lipoprotein
LOCF	Last observation carried forward
LOQ	Limit of quantitation
mAb	Monoclonal antibody
MedDRA	Medical Dictionary for Regulatory Activities

MI	Multiple imputation
NAb	Neutralizing antibody
NCA	Non-compartmental analysis
NRS	Numeric rating scale
ObsRO	Observation reported outcome
OLE	Open-label extension
PASQ	Pediatric Asthma Symptom Questionnaire
PCSV	Potentially clinically significant value
PD	Pharmacodynamic
PK	Pharmacokinetic
PPS	Per protocol set
POEM	Patient Oriented Eczema Measure
PRO	Patient reported outcome
PT	Preferred term
PV	Phone visit
Q1	First quartile
Q2W	Every 2 weeks
Q3	Third quartile
Q4W	Every 4 weeks
QOL	Quality of Life
QW	Once weekly
RBC	Red blood cell
Regeneron	Regeneron Pharmaceuticals, Inc.
SAE	Serious adverse event
SAF	Safety analysis set
SAP	Statistical analysis plan
SAS	Statistical Analysis Software
SC	Subcutaneous
SCORAD	SCORing Atopic Dermatitis
SCN	Screening
SD	Standard deviation
SMT	Safety monitoring team

SOC	System organ class
TARC	Thymus and activation regulated chemokine
TB	Tuberculosis
TCI	Topical calcineurin inhibitor
TCS	Topical corticosteroids
TEAE	Treatment-emergent adverse event
Th2	Type 2 helper T cell
ULN	Upper limit of normal
US	United States
V	Volume of distribution
WBC	White blood cell
WOCF	Worst observation carried forward

1. INTRODUCTION AND RATIONALE

1.1. Introduction

Atopic dermatitis (AD), also known as atopic eczema, is a pruritic skin condition characterized by a chronic, relapsing form of skin inflammation, a disturbance of the epidermal-barrier function associated with immune changes in the skin, and a high prevalence of immunoglobulin E (IgE) mediated sensitization to food and environmental allergens ([Bieber 2008](#)).

Atopic dermatitis is one of the most common skin disorders in infants and children ([Mortz 2015](#)). The prevalence of AD in the first 2 years of life has been reported to be 21.5% ([Ileli 2004](#)). Phase 3 of the International Study of Asthma and Allergies in Childhood showed a 1-year period prevalence rate higher than 15% in the 6 to 7-year-old age group in Australia, England, and Scandinavia ([Asher 2006](#)). The clinical pattern of AD varies with age. Infants typically present with erythematous papules and vesicles on the cheeks, forehead, or scalp, which are exudative and intensely pruritic. The childhood phase typically occurs from 2 years of age to puberty. Children present with lichenified papules and plaques representing the more chronic disease involving the hands, feet, wrists, ankles, and antecubital and popliteal regions. In adults, predominant areas of involvement include the flexural folds, the face and neck, the upper arms and back, and the dorsa of the hands, feet, fingers, and toes. The eruption is characterized by dry, scaling erythematous papules and plaques, and the formation of large lichenified plaques from lesional chronicity.

The disease has been shown to have a marked impact on the quality of life (QOL) of pediatric patients, greater than that seen in other common skin disorders like psoriasis and urticaria ([Beattie 2006](#)). A study comparing the impact on the QOL of family members of children suffering from eczema and type 1 diabetes found that all families of children with moderate-to-severe eczema had significantly higher impact scores than those of diabetic children ([Su 1997](#)). Often, severe pruritus is a universal finding in AD and often results in sleep disruption, irritability, and generalized stress for both the affected patients as well as family members ([Kim 2012](#)).

Of particular interest in younger children is the phenomenon of “Atopic March” which is characterized by a typical sequence of progression of clinical signs of atopic disease. In general, the clinical signs of AD and of food allergies predate the development of asthma and allergic rhinitis, suggesting that AD is an “entry point” for subsequent allergic disease ([Spergel 2003](#)). Severity of AD is correlated with development of asthma and allergic rhinitis ([Zheng 2011](#)).

Infants and young children with severe AD have a reported risk rate of around 60% for developing asthma later on in life compared to a risk of around 30% in patients with mild AD ([Ricci 2006](#)).

Atopic dermatitis is caused by a complex interaction of genetics, defects in skin barrier function, environmental exposure, and immunologic responses. Type 2 helper T cell (Th2) mediated immune response is believed to play a central role in the pathogenesis of AD. The skin lesions of AD are characterized by increased expression of proinflammatory Th2 cytokines, such as interleukin (IL)-4 and IL-13, and by skin infiltration of Th2 cells. The elevated IgE responses and eosinophilia observed in the majority of patients with AD reflects an increased expression of the Th2 cytokines IL-4 and IL-13 ([Leung 1999](#)). Type 2 helper T cell-associated cytokines regulate important barrier related functions, such as epidermal cornification and production of antimicrobial proteins. These cytokines inhibit the production of major terminal differentiation proteins, such as loricrin, filaggrin, involucrin, and the antimicrobial proteins human beta defensin 2 and 3, which in turn, is associated with development of AD ([Howell 2007](#), [Guttman Yassky 2011a](#), [Guttman Yassky 2011b](#)).

The Th2 cytokines also act on keratinocytes and induce production of chemokines, including chemokine (C-C motif) ligand 17 (also known as thymus and activation regulated chemokine [TARC]), and chemokine (C-C motif) ligand 26 (also known as eotaxin-3), which are chemo-attractants for Th2 cells and eosinophils; thus, perpetuating the inflammatory response. Since activation of IL-4 and IL-13 signaling precedes the release of proinflammatory mediators, antagonism of these cytokines has the potential to reduce the Th2 response and provide therapeutic benefit.

A study was recently conducted with the aim of identifying differences and similarities between cutaneous lymphocyte antigen (CLA) +ve, polarized T-cell subsets in children versus adults with AD. In this study, peripheral blood from children less than 5 years old was compared with that of adults with well-characterized moderate-to-severe AD, using flow cytometry. The study concluded that Th2 activation within skin-homing T cells might drive AD in children. Moreover, the spreading to additional Th subsets, particularly Th22, is seen in adults but not in children ([Czarnowicki 2015](#)). Based on the results of this study, it is speculated that therapeutics that target Th2 cytokines, such as dupilumab, might be particularly valuable in the pediatric population with AD.

There is currently a high unmet medical need for an effective therapy for AD with an acceptable safety profile in infants and young children who suffer with moderate-to-severe AD. Nonpharmacological management of AD, which includes environmental control measures (eg, avoidance of antigen and skin irritants) and skin care measures (eg, maintaining the hydration of the skin through the use of emollients) play a supportive role, especially in children with moderate-to-severe disease. Pharmacological management of AD in children is mainly limited to topical therapy with topical corticosteroids (TCS) and topical calcineurin inhibitors (TCIs). However, long-term use of TCS in children is not recommended because of the risk of irreversible skin atrophy, dyspigmentation, acneiform eruptions, and risks associated with systemic absorption (eg, growth retardation, hypothalamic pituitary axis effects, etc). Topical calcineurin inhibitors, such as tacrolimus and pimecrolimus, are also used in AD as an alternative to or in combination with TCS. However, both tacrolimus and pimecrolimus are not indicated for use in children <2 years of age. Moreover, the use of TCI is frequently associated with skin irritation. Furthermore, a possible increased risk of malignancy (lymphoma and skin cancers) has been noted for TCIs.

Systemic agents are used off-label in children (cyclosporine, systemic steroids, methotrexate, azathioprine, and mycophenolate mofetil). A recent survey conducted in Europe, “European

Treatment of Severe Atopic Eczema in Children Taskforce (TREAT)" found that approximately 70% of respondents initiated systemic therapy for children with severe AD (Proudfoot 2013). All of these systemic agents have significant side effects in children, including stunted growth, diabetes, hypertension, osteoporosis (corticosteroids), myelosuppression and hepatotoxicity (methotrexate), nephrotoxicity and hypertension (cyclosporine), and gastrointestinal disturbances and leucopenia (azathioprine). Moreover, a high proportion of patients in which disease is initially controlled by systemic agents suffer from relapse soon after therapy is discontinued (Schmitt 2009).

Type 2 inflammation (including Th2 responses) and the dysregulated activation of Th2 cells have been recognized as the key underlying disease drivers of AD and other associated atopic/allergic diseases. Targeting the key upstream type 2 cytokines, IL-4 and IL-13, has the potential for treating the pathology of AD as well as other associated atopic/allergic diseases. Since activation of IL-4 and IL-13 signaling precedes the release of proinflammatory mediators, antagonism of these cytokines has the potential to reduce the type 2 inflammatory responses seen in AD and other associated atopic/allergic diseases. In addition, type 2/Th2 cytokines are believed to induce altered epidermal responses, inhibit terminal differentiation proteins, and produce and/or amplify the skin barrier defect in AD; therefore, antagonism of IL-4 and IL-13 signaling has the potential to restore barrier function.

Dupilumab is a novel targeted immunoregulatory agent that selectively and simultaneously inhibits IL-4 and IL-13 signaling by blocking the obligate shared component of the IL-4/IL-13 receptor complex. It is intended to inhibit key disease drivers to achieve clinical benefit without the side effects commonly observed with existing non-selective systemic immunosuppressants. Dupilumab has been approved for marketing in the US, EU, and Japan for treatment of moderate-to-severe AD in adults and adolescents.

Dupilumab, given subcutaneously (SC), is currently in clinical trials for multiple indications, including treatment of moderate-to-severe AD in patients intolerant of, or whose disease is not adequately controlled with, topical treatments. As of 28 March 2019, dupilumab clinical data in AD are available from 22 completed and 6 ongoing (phase 1, 2, and 3) studies in adult healthy subjects and in patients with AD. A total of 202 healthy subjects, and 3931 patients with AD have been exposed to dupilumab in phase 1, single-dose studies at doses up to 12 mg/kg intravenous (IV) and 600 mg SC, and phase 1 through 3 multiple-dose studies at doses up to 300 mg once a week (QW), preceded by a 600 mg loading dose. Sixteen of the 22 completed studies were conducted in patients with AD. Data from these studies showed rapid and dose-dependent improvement in pharmacodynamic (PD) and efficacy endpoints in dupilumab-treated patients. Dupilumab has also been consistently well-tolerated across these clinical studies.

Dupilumab has been studied in 2 completed studies in pediatric patients with AD. R668-AD-1412 was a phase 2 study investigating the safety, pharmacokinetics (PK), immunogenicity, and exploratory efficacy of dupilumab in patients aged ≥ 6 to < 12 years with severe AD and ≥ 12 to < 18 years with moderate-to-severe AD (77 patients were exposed to dupilumab). R668-AD-1526 was a phase 3 study investigating the efficacy and safety of dupilumab in patients ≥ 12 to < 18 years of age with moderate-to-severe AD (166 patients were exposed to dupilumab). Data from these completed studies in pediatric patients with AD showed that dupilumab had an acceptable safety profile and was well tolerated in patients aged ≥ 6 to < 18 years of age (see Section 1.2.3.2), and provided significant clinical benefit (Section 1.2.3.1).

In addition, dupilumab is currently being studied in 2 other ongoing pediatric studies: a phase 3 study (R668-AD-1652) investigating the efficacy and safety of dupilumab administered concomitantly with TCS in patients 6 years to <12 years of age with AD, and an open-label extension (OLE) study (R668-AD-1434) to assess the long-term safety and efficacy of dupilumab in patients aged \geq 6 months to <18 years with AD. Study R668 AD 1652 has completed the primary analysis period and the OLE study R668-AD-1434 has completed the secondary analysis period.

Dupilumab has also been studied in 2 completed (EFC13579 and EFC13691) and 1 ongoing (EFC14153) phase 3 double-blind, placebo-controlled studies evaluating the efficacy and safety of dupilumab in patients, including pediatric patients, with uncontrolled asthma (see Section 1.2.3.2).

In addition, pediatric patients aged \geq 12 to <18 years (n=50) were included in study R668-AD-1607 (a phase 1b actual use study of dupilumab auto-injector device in patients with AD).

Completed and ongoing clinical studies with dupilumab in AD are further described in Section 1.2.3.

Additional background information on the study drug and development program can be found in the Investigator's Brochure.

